#### **8.8.1.2 Demographic and Other Baseline Characteristics**

Demographic characteristics will be listed. Demographic characteristics will be summarized using appropriate descriptive statistics, as applicable. Details of the summaries to be produced will be included in the statistical analysis plan.

#### **8.8.1.3 Efficacy Variables**

##### **Definition of Primary Efficacy Endpoint - ACR20 at Week 12**

The primary endpoint is the percentage of subjects achieving an ACR20 response at Week 12. Other time points will be regarded as secondary endpoints.

The ACR response is a measurement of improvement in multiple disease assessment criteria. The ACR20 response is defined as:

≥20% improvement from Baseline in SJC66 (66 joints) and TJC68 (68 joints)

AND

CONFIDENTIAL

≥20% improvement from Baseline in at least 3 of the following 5 assessments

- Pain (VAS) in cm (from HAQ-DI).
- Patient's Global Assessment of Disease Activity (VAS) in cm.
- Physician's Global Assessment of Disease Activity (VAS) in cm.
- Patient's Assessment of Physical Function as measured by HAQ-DI.
- CRP in mg/dL or mg/L.

### **Definition of Secondary Efficacy Endpoints**

#### **ACR50 and ACR70**

ACR50 and ACR70 are similarly defined as ACR20, except the improvement threshold from Baseline is 50% and 70%, respectively.

#### **ACR-N**

The ACR-N is the smallest percentage improvement in swollen and tender joints and the median of the remaining 5 core parameters, and is expected to be more sensitive to change than the ACR20, ACR50 or ACR70.

ACR-N = MIN [%improvement in TJC68,  
%improvement in SJC66,  
MED %improvement in (patient's global assessment, physician's  
global assessment, patient's assessment of pain, HAQ-DI, CRP)]

#### **ACR/EULAR Remission**

A subject's disease activity status can be defined as being in remission:

when scores on the TJC28, SJC28, CRP (actual value in mg/dL) and Patient Global Assessment of Disease Activity (cm) are all ≤1.

#### **Simplified Disease Activity Index (SDAI)**

The SDAI is the numerical sum of 5 outcome parameters: TJC28, SJC28, Patient Global Assessment of Disease Activity (in cm), Physician's Global Assessment of Disease Activity (in cm), and CRP (mg/dL).

SDAI = TJC28 + SJC28 + Patient's Global Assessment of Disease Activity (VAS in cm) + Physician's Global Assessment of Disease Activity (VAS in cm) + CRP (mg/dL)

The SDAI can be categorized:

- High disease activity: SDAI >26
- Moderate disease activity: [11,26]
- Low disease activity: [3.3,11]
- Remission: ≤3.3

#### **Clinical Disease Activity Index (CDAI)**

The CDAI is the SDAI modified to exclude CRP.

CDAI = TJC28 + SJC28 + Patient's Global Assessment of Disease Activity (VAS in cm) + Physician's Global Assessment of Disease Activity (VAS in cm)

The CDAI can also be categorized:

- High disease activity: >22
- Moderate disease activity: [10,22]
- Mild disease activity: [2.8,10]
- Remission: ≤2.8

### Disease Activity Score 28 Joints Corrected for CRP (DAS28[CRP])

The DAS28(CRP) is a statistically derived index combining tender joints (28 joints), swollen joints (28 joints), CRP and Patient's Global Assessment of Disease Activity (general health, GH). DAS28(CRP) is defined as follows:

$$\text{DAS28(CRP)} = 0.56 \times \text{SQRT(TJC28)} + 0.28 \times \text{SQRT(SJC28)} + 0.36 \times \text{Ln(CRP+1)} + 0.014 \times \text{GH} + 0.96,$$

Where:

TJC28 is 28 joint count for tenderness

SJC28 is 28 joint count for swelling.

Ln(CRP+1) is the natural logarithm of (CRP value [mg/L] + 1)

SQRT is square root

GH is the Patient's Global Assessment of Disease Activity on a 100 mm VAS

Categorization of the DAS28(CRP) scores:

High disease activity: >5.1

Moderate disease activity: [3.2,5.1]

Low disease activity: [2.6,3.2]

Remission: <2.6

### EULAR Response

A second categorization of the DAS28(CRP) will be done according to the following table:

| Actual DAS28(CRP) | Improvement in DAS28(CRP) from Baseline: |               |       |
|-------------------|--|---------------|-------|
|                   | > 1.2                                    | > 0.6, ≤ 1.2] | ≤ 0.6 |
| ≤ 3.2             | Good                                     | Moderate      | None  |
| > 3.2, ≤ 5.1]     | Moderate                                 | Moderate      | None  |
| > 5.1             | Moderate                                 | None          | None  |

## Quality of Life - FACIT Fatigue Scale and SF-36

Quality of life will be assessed using the FACIT fatigue scale and the SF-36 questionnaire. The appropriate (sub)totals will be derived according to the scale's scoring algorithm.

### **Methods of Analysis**

Efficacy data (ACR20, ACR50, ACR70, ACR-N, DAS28(CRP), EULAR response, and ACR/EULAR remission, and components of the ACR, CDAI and SDAI at each post-dosing visit) will be analyzed descriptively.

Between-group comparisons will be done for each dose group versus the placebo group. Hommel's closed-testing correction procedure (as implemented in SAS PROC MULTTEST) will be applied to adjust for multiplicity.

This study is not powered for any formal comparison among the dose groups, nor for comparisons between q.d. and b.i.d. regimens. However, differences between q.d. and b.i.d. regimens will be calculated and presented with a 95% confidence interval. Differences between q.d. and b.i.d. regimens will also be tested exploratively via a model containing the total daily dose (50/100/200 mg) as well as the regimen (q.d./b.i.d.). Differences among the q.d. groups and among the b.i.d. groups will be described in the same way. No adjustment for multiplicity will be done for these exploratory differences.

Nonresponding subjects from the placebo and lowest dose groups who are re-randomized at Week 12 will be handled as follows:

- Their Week 12 value will be carried forward in the original treatment group to all further time points (and between-group comparisons) after Week 12.
- Their actual assessments on Weeks 16, 20 and 24 will be analyzed descriptively as these represent their response after 12 weeks of GLPG0634 exposure after first having failed on placebo or a low dose.

Analysis methods per post-Baseline time point:

- Binary parameters: logistic regression model with factors treatment, region and previous use of biologics.
- Continuous parameters: changes from Baseline and percent changes from Baseline: using an analysis of (co)variance model with factors treatment, baseline value, region and previous use of biologics.
- Time to response (ACR20/50/70) will be analyzed using Kaplan-Meier survival techniques, and groups will be compared against placebo using a Cox proportional hazards regression model with factors treatment, region and previous use of biologics.

Other applicable factors, if any, will also be included in the models. Quality of Life data (FACIT fatigue scale and SF-36 questionnaire) will be analyzed descriptively. Exploratory between-group comparisons will also be done at each post-Baseline time point using analysis of (co)variance models on the changes from Baseline with factors treatment, Baseline value, region and previous use of biologics.

Handling of discontinued subjects during the 24-week treatment period:

CONFIDENTIAL

- Subjects who discontinue within the first week so that ACR20/50/70 responses cannot be determined will be classified as nonresponders.
- For all discontinued subjects, their last observed nonmissing result will be used in the subsequent visits (last observation carried forward algorithm). Also for the ACR20/50/70 responses as part of the secondary/supportive analyses.

A descriptive sensitivity analysis by country, geographic region and previous use of biologics will be performed for the ACR criteria response rates.

Further exploratory analyses may be added when deemed useful to understand the data.

Graphical presentations may be added to facilitate the overall interpretation of the study results.

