### **4.4.3. Handling of missing values and early dropouts in the efficacy analyses during the first study period (up to Week 12)**

This is for the “efficacy chapter 2” analysis.

For binary data (e.g., ACR20), two different imputations will be done for missing visits as well as early dropouts: non-responder imputation (NRI) and LOCF, up to and including Week 12. The NRI imputation will be primary, and LOCF will be secondary.

For other data (ordinal or continuous), missing visits as well as early dropouts will be imputed using the last observation carried forward (LOCF) algorithm, up to and including Week 12.

Definitions of the imputation methods:

- LOCF (all types of parameters, from binary to continuous): to impute a missing value, the last preceding nonmissing value will be used (which could even be a baseline value).
- NRI (binary response parameters only): to impute a missing response, the subject will be assumed to be a non-responder.

For all parameters, an observed-case analysis will also be performed (i.e., without any imputation). The observed-case analysis will serve as a sensitivity analysis (to ascertain the impact of early dropouts on the results) and will basically be limited to:

- ACR20/50/70/N: descriptive at W12+W24 and inferential at W12
- EULAR remission: descriptive at W12+W24
- SDAI/CDAI: descriptive at BSL+W12+W24
- DAS28: descriptive at BSL+W12+W24 and inferential at W12
- All ACR components (VAS, joint counts, CRP, HAQ-DI): descriptive at BSL+W12+W24
- QoL (FACIT,SF-36): descriptive at BSL+W12+W24.

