## 6.1.2. Efficacy Variables

### 6.1.2.1. Definition of primary efficacy endpoint: ACR20 at Week 12

The primary endpoint is the percentage of subjects achieving an ACR20 response at Week 12. Other time points will be regarded as secondary endpoints. The non-responder imputation (NRI) of the ACR20 will be the primary parameter, with observed-case and last observation carried forward (LOCF) imputation as secondary confirmatory analyses.

The ACR response is a measurement of improvement in multiple disease assessment criteria. The ACR20 response is defined as:

≥20% improvement from baseline in SJC66 (66 joints) and TJC68 (68 joints)

AND

≥20% improvement from baseline in at least 3 of the following 5 assessments

- Pain (VAS) in cm (from HAQ-DI).
- Patient's Global Assessment of Disease Activity (VAS) in cm.
- Physician's Global Assessment of Disease Activity (VAS) in cm.
- Patient's Assessment of Physical Function as measured by HAQ-DI.
- CRP in mg/L.

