**Note that the primary endpoint of the study is the ACR20 at Week 12 in the ITT population, using NRI imputation.**

The ACR-N is derived using the following formula:

$$\text{ACR-N} = \text{MIN} [ \% \text{ improvement in TJC68, } \% \text{ improvement in SJC66, MED } \% \text{ improvement in (patient's global assessment, physician's global assessment, patient's assessment of pain, HAQ-DI, CRP) } ]$$

So this is taking the smallest of the percentage increases in SJC66, TJC68, and the third of the remaining 5 parameters. In case the ACR-N is negative (i.e., the subject actually worsens instead of improves), then the ACR-N is replaced by a 0. The ACR-N is therefore a number between 0 and 100.

The ACR-N represents the percentage NN% according to which the subjects would have been an "ACRNN" responder.

(See further sections on how to derive these components.)

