#### 8.4.2. Tables over the whole 24 weeks period

Tables will present Baseline-Weeks 1-2-4-8-12-16-20-24, unless specified otherwise. A similar analysis as to SDAI and CDAI will be performed. Analysis population: ITT. LOCF and observed case (descriptive at Baseline, Week 12 and Week 24; inferential statistics only at Week 12).

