**Table 14.2.1.4.15: DAS28(CRP) EULAR response: Frequency table**

Frequency per time point, and per treatment group. EULAR response will be presented in the categories defined above (none, moderate, good).

Overall p-value and pairwise comparisons versus placebo: Cochran-Mantel-Haenszel test for row mean score differences, controlling for region and prior biologics. These p-values will be corrected for multiplicity according to Hommel’s closed-testing method as implemented in SAS PROC MULTTEST. The uncorrected p-values will also be presented.

Population: ITT and per-protocol.

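### EULAR response and ACR-N have no analysis that counts withdrawal as failure, so a subject who withdraws early while responding can keep that response there while failing on ACR20/50/70

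*Protocol*

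**What the plan says.** Protocol section 8.8.1.3 (Methods of Analysis) sets a general rule: "For all discontinued subjects, their last observed nonmissing result will be used in the subsequent visits (last observation carried forward algorithm". The next sentence extends it: "Also for the ACR20/50/70 responses as part of the secondary/supportive analyses". The protocol does not name NRI. That comes from the SAP.

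SAP section 4.4.3 sets the imputation method by type of variable. For binary data: "The NRI imputation will be primary, and LOCF will be secondary". For the rest: "For other data (ordinal or continuous), missing visits as well as early dropouts will be imputed using the last observation carried forward". Section 4.4.4 repeats both rules up to Week 24, and section 6.1.2.3 summarises them. For the primary endpoint, section 6.1.2.1 says: "The non-responder imputation (NRI) of the ACR20 will be the primary parameter".

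The two endpoints at issue fall on the non-binary side:

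- **EULAR response** is analysed in Tables 14.2.1.4.15 to 17, where "EULAR response will be presented in the categories defined above (none, moderate, good". These tables sit in SAP section 8.4.2, whose imputation rule is "LOCF and observed case (descriptive at Baseline, Week 12 and Week 24; inferential statistics only at Week 12". The comparisons with placebo use a Cochran-Mantel-Haenszel row mean score test with Hommel correction.
- **ACR-N** is analysed in Tables 14.2.1.1.12 to 14 by ANOVA, with LOCF and observed case only. The comparisons with placebo are Hommel-corrected.

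By contrast, the DAS28(CRP) remission table is specified with NRI, LOCF and observed case, and the table for remission or low disease activity (14.2.1.4.12) follows it.

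**The concern.** Both endpoints have a natural failure value, *none* for EULAR response and 0 for ACR-N, but no planned analysis assigns it to a subject because of withdrawal. LOCF keeps the last result. Observed case drops the subject, and it is tested at Week 12 only.

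The report could then give opposite verdicts on the same subject. Someone who withdraws around Week 4 with an ACR-N of 60 is a non-responder on ACR20 and ACR50 at Week 12 under the primary rule, yet contributes 60 to the ACR-N mean and may count as a good EULAR responder.

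Protocol section 8.3.4 requires withdrawal for serious infections and for several laboratory limits, whatever the efficacy response. If such withdrawals were more frequent at higher doses, among subjects who were responding, LOCF would favour those doses on these endpoints. ACR-N is also part of the Week 12 interim output that supports phase III dose selection.

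**Working it through.** **The plan's own figures.** The documents give no figure for this point and no withdrawal rate. The arm size of 85 comes from Protocol section 8.8.2. The power stated there reproduces with a two-sided chi-square test at alpha 0.05/6: 0.898 (48% vs 20%) and 0.912 (70% vs 40%) against 90%, and 0.809 (45% vs 20%) and 0.784 (66% vs 40%) against 80%. The concern does not depend on these values.

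**Are the endpoints really measuring the same response?**

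1. ACR-N is the minimum of the TJC68 improvement, the SJC66 improvement and the median of the other five improvements (SAP section 8.1.1). If ACR-N is at least 20, both joint counts improved by at least 20%, and so did at least three of the other five measures. That is the ACR20 definition. The SAP says so itself: "The ACR-N represents the percentage NN% according to which the subjects would have been an" ACRNN responder. The ACR-N bands in Table 14.2.1.1.12 at 20, 50 and 70 therefore accumulate to LOCF versions of the ACR20/50/70 rates.
2. A good EULAR response needs DAS28(CRP) of at most 3.2 and an improvement above 1.2 (SAP section 8.4.1). Remission is below 2.6 and low disease activity is 2.6 to 3.2, so every good responder is also in remission or low disease activity. A subject withdrawn early in that state fails in the NRI version of Table 14.2.1.4.12 and is *good* in Table 14.2.1.4.15 under LOCF.

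**Who is affected.** SAP section 3.3 places early discontinuation visits in time windows. A visit on Days 71-98 is observed Week 12 data, and one on Days 155-182 is observed Week 24 data, for every endpoint including ACR20. The split concerns earlier withdrawals only.

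**Size within one arm (rates assumed).** Let d be the share withdrawing before the window, and r the share of those who were good or moderate EULAR responders at their last visit. LOCF exceeds NRI by d x r:

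- d = 2%: 0.02 x 0.30 = 0.6 to 0.02 x 0.70 = 1.4 points
- d = 5%: 1.5 to 3.5 points
- d = 10%: 3.0 to 7.0 points
- d = 15%: 4.5 to 10.5 points, or about 4 to 9 subjects of 85

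For ACR-N, setting withdrawn subjects to 0 lowers the arm mean by d x (mean carried value). With an assumed carried mean of 20-40, this runs from 0.02 x 20 = 0.4 to 0.15 x 40 = 6.0 units.

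**Size in the difference from placebo (rates assumed).** The excess of LOCF over NRI is dA x rA - dP x rP, for active (A) and placebo (P):

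- Equal dropout: 0.08 x (0.40 - 0.30) = 0.8 points; 0.15 x (0.70 - 0.20) = 7.5 points
- More dropout on active: 0.12 x 0.50 - 0.06 x 0.25 = 4.5 points; 0.12 x 0.60 - 0.06 x 0.30 = 5.4 points
- More dropout on placebo: 0.04 x 0.40 - 0.12 x 0.30 = -2.0 points

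The sign depends on the dropout pattern.

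**Week 12 switchers.** SAP section 4.5.1 regards placebo, 50 mg q.d. and 25 mg b.i.d. subjects who switch at Week 12 as having discontinued. Section 6.1.2.3 carries their Week 12 value forward. For ACR20 the two routes agree, because a switcher missed the joint-count criterion and is already a non-responder. For the endpoints here they do not: a switcher may be a moderate EULAR responder or have an ACR-N between 0 and 20. Setting switchers to failure would act on those three arms only. If 40-60% of placebo switch with a mean Week 12 ACR-N of 3-8 (assumed), the placebo mean falls by 0.40 x 3 = 1.2 to 0.60 x 8 = 4.8 units, which is comparable with the shift from true withdrawals.

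**The case against.** The rule is explicit and applied consistently by variable type, and nothing in the documents contradicts it. Protocol section 6.6 presents ACR-N as a continuous measure of the magnitude of benefit, so LOCF there is a recognisable choice. Withdrawal as failure is already tested on closely related endpoints: ACR20/50/70 and DAS28(CRP) remission or low disease activity all have NRI analyses. A dose flattered by LOCF would show as a gap against those tables. Both endpoints are secondary.

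Most of this stands and limits the weight of the point. It does not supply the missing analysis for EULAR response itself, which is a response classification tested in its own right. The tables that would expose the gap cover the *good* category but not *moderate*.

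A reader might go further and infer that subjects who stop for toxicity count as responders on two tested endpoints. The documents do not support that. LOCF carries whatever was last seen, including no response or even a baseline value. ACR-N carries a magnitude, not a responder status. ACR20/50/70 also have supportive LOCF and observed-case analyses. No imputation rule depends on the reason for withdrawal.

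A reader might also infer that higher doses are flattered and that dose selection is exposed. No dropout rate or last-visit response rate is given, and lack of improvement is itself a listed reason for stopping, so placebo withdrawals could be the more frequent. EULAR response is not among the interim outputs. ACR-N appears there beside NRI ACR20/50/70, termination reasons by arm and adverse events leading to discontinuation.

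**Conclusion.** The gap is real and limited. EULAR response and ACR-N are analysed only by LOCF and observed case, so a subject who withdraws before the analysis window while responding can keep that response on both, while failing in the NRI analyses of ACR20/50/70 and of DAS28(CRP) remission or low disease activity. The primary ACR20 test is untouched.

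Under assumed withdrawal of 2-15% with 30-70% responding at last visit, an arm's good-or-moderate EULAR rate moves by about 1 to 10 points. The effect on the difference from placebo ranged from -2.0 to 7.5 points in the scenarios tried, so neither its size nor its direction can be settled from the documents.

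The change is cheap and worth making. For EULAR response it extends a rule that the SAP already treats as primary for binary responses. For the continuous ACR-N, replacing LOCF as the main method is a trade-off, so a sensitivity analysis is enough.

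**What to change.** - **EULAR response (Tables 14.2.1.4.15 to 17):** add an NRI analysis in which missing or withdrawn is scored *none*, and make it the main analysis, as for the binary response endpoints. Keep LOCF and observed case as supportive.
- **ACR-N (Tables 14.2.1.1.12 to 14):** add a sensitivity analysis that sets ACR-N to 0 for withdrawn subjects. Keep LOCF as the main analysis.
- **Switchers:** state that subjects who switch treatment at Week 12 are not withdrawn for this purpose and keep their carried-forward Week 12 value, as in SAP section 6.1.2.3. Without this sentence, placebo and the two lowest-dose arms alone would be pushed towards failure after Week 12, which could favour the higher doses.

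The cost is SAP wording and one extra imputation run per table. EULAR results may come out slightly less favourable.

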#### **8.8.1.4 Safety Variables**

Clinical safety will be evaluated by assessing treatment-emergent AEs, physical examinations, laboratory assessments, ECG, and vital signs results in a descriptive manner. Original results and changes from Baseline or from Screening, for the ECG, will be summarized for the laboratory data, vital signs, and ECG values. Values will be categorized as low/normal/high according to normal ranges, and shift tables versus baseline will be created to determine treatment-emergent abnormalities.

#### **8.8.1.5 Interim Analyses**

A fully unblinded interim analysis will be performed when all subjects have reached Week 12. The statistical analysis of the unblinded data will be handled by a statistician who is independent from the regular study team. The lead statistician and corresponding biometrics team will remain blinded and will not be involved in the interim analyses in order to preserve blinding when assessing the final results at Week 24.

This interim analysis output will comprise summary tables and plots, but no listings. These summary results will be viewed by the sponsor, but no individual subject data (such as listings or datasets) will be exchanged. The analysis will summarize demographics, reason for early discontinuation from the study, efficacy (i.e., ACR20, ACR50, ACR70, ACR-N, DAS28[CRP] with low disease activity, CDAI/SDAI with low disease activity, CRP, and HAQ-DI) and safety (i.e., AE, SAE, and selected laboratory tests).

The interim analysis is intended to support preliminary dose-selection for the GLPG0634 phase III program. Because this efficacy analysis matches the full Week 12 primary analysis, there is no inflation of the type-I error rate, and therefore no statistical correction is applied.

### **8.8.1.6 Pharmacokinetic Analyses**

GLPG0634 and G254445 plasma concentrations will be analyzed by nonlinear mixed-effects modeling (NONMEM program) to determine the population PK parameters as well as covariates influencing the PK in RA subjects. The population PK analysis will be reported separately. Additional analyses (e.g. on MTX and its metabolite) might be performed.

